8.6 Secondary Endpoint(s)

The socio-demographic characteristics of the patients, the history of their disease, the context of the diagnosis, the medical history, the clinical evaluation criteria of liver and spleen, the MRI evaluation criteria of the liver and spleen, the MRI evaluation criteria of bone lesions and the biological evaluation criteria are described by mean and standard deviation for quantitative variables, by frequency and percentage for categorical and ordinal variables. The 95% confidence intervals will be calculated. The evolutions of these criteria at the different periods when they are collected are described by mean and standard deviation or percentage changes. They are compared between the different times of the study by test on repeated data: ANOVA on repeated series or Wilcoxon rank test, depending on the nature and distributions of the studied variables

The analysis will describe and analyze the evolution of bone disease on the basis of the MRI's measures. It will describe and analyzes also the evolution of patients on the basis of their other MRI measures, clinical and laboratory data. It will describe also the incidence of spleen infarcts, fibrosis, liver nodules and their evolution under treatment by velaglucerase alfa.

Comparisons shall be made by analysis of variance on repeated series for quantitative variables or by Wilcoxon signed rank tests if normality is not demonstrated and by McNemar tests or rank tests on repeated series for quantitative or ordinal criteria

Changes over time in hepatomegaly, presence of lithiasis, nodules or infarct will be analysed using macNemar test and changes in liver measurements will be compare using analysis of variance on repeated series,

Changes over time in splenomegaly, presence of nodules or infarct will be analysed using Mac Nemar test and changes in spleen measurements will be compare using analysis of variance on repeated series,

Change in marrow infiltration, bone infarction, osteonecrosis, pathological fractures vertebral will be analysed using Mac Nemar test or Wilcoxon rank test.

Changes in fatigue, abdominal pain, bone pain: hemorrhagic syndrome, lung disease and neurological disease will be analysed using Mac Nemar test or wilcoxon rank test

Changes over time of biological parameters (hemoglobinemia, leucocytes, platelets count, SGOT, SGPT, Gamma GT, alkalin phosphatases, converting enzyme angiotensin, ferritin, chitriosidase, gamma globulins, IgG, IgA, IgM, calcium level, D vitamin, B12 vitamin, triglycerides, cholesterol, monoclonal peak) will be analysed using variance analysis on repeated series.

Logistic regression type shall be used to determine criteria influencing positive or negative evolutions. The analysis on MRI parameters will be conducted successively on all MRI assessable and on optimal quality MRI only.

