3.2 Secondary Endpoint(s)

The secondary and exploratory endpoint(s) of this study are:

- socio-demographic characteristics: age, sex, occupation
- history of the disease and context of diagnosis: age at diagnosis, type of symptoms, exams that allowed the diagnosis and its confirmation, enzymatic assay value, genotype and presence or absence of family history
- medical history
- clinical evaluation criteria: weight (kg), height (cm), absence or presence (mild, moderate or severe) asthenia, abdominal pain, chronic bone pain, bone crises, syndrome bleeding, pulmonary impairment, neurological impairment
- clinical endpoints of liver and spleen:
 - Absence or presence of hepatomegaly, with the extent of the arrow (medio-clavicular line) (cm)
 - Absence or presence of splenomegaly, with the extent of the costal overhang (cm).-
- liver evaluation criteria and spleen MRI:
 - Absence or presence of hepatomegaly, with the extent of the arrow (medio-clavicular line) (cm)
 - Absence or presence of splenomegaly, with the extent of the costal overhang (cm)
 - Liver volume (m3)
 - Spleen volume (m3)
 - Presence or absence of myocardial, nodules, fibrosis, vesicular stones or other alterations.
- evaluation criteria of bone lesions by MRI (spine, pelvis, femurs, tibias and other symptomatic localization)

Absence or presence of bone lesions and their locations: bone infiltration, cortical thinning, osteonecrosis, bone infarction, stroke sequelae, vertebral compression fracture or other bone disease
- evaluation criteria of the biological parameters: hemoglobin (g/dl); leukocytes (cells/mm3); platelets (mm3); ACE (angiotensin converting enzyme (U/l); ferritin (mg/l); chitotriosidase (nmol/ h/ ml); CCL18 (ng/ml), vitamin D (nmol/L), vitamin B12 (pmol / l); SGOT / AST (U/l), SGPT / ALT (U/l), GGT (U/l), alkaline phosphatase (U/l), triglycerides (mmol/l), total cholesterol (mmol/l) gamma globulin (g/l) serum calcium (mmol/l) presence or absence of a monoclonal peak and the type if any

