6.5 Demographics

Patient demographic information including gender, age, and professional status will be collected as soon as the patient is included in the observational study. The age that will be collected is the age of patient at VPRIV® treatment initiation.

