6.7 Efficacy and Effectiveness Assessments

For the closest MRI realized before the initiation of VPRIV® treatment and for each MRI which will be conducted during the prospective one year period, the following information will be recorded whenever they are available in patient's dossiers. Clinical and biological status will also be recorded when treatment was started and the patient included in the study.

- Spine and femur BMB score of T1 and T2 weighted,
- Marrow infiltration, bone infarction, osteonecrosis, pathological fractures (vertebral)

The clinical status:

***Retrospective and prospective observational study of MRI changes in bone and visceral lesions of patients with type 1
Gaucher disease treated with VPRIV® (velaglucerase alfa)***

- Height, weight
- Asthenia (absent / present : mild , moderate or severe), abdominal pain (absent / present : mild , moderate or severe), chronic pain in bone (absent / present : mild , moderate or severe), hemorrhagic syndrome (epistaxis, gingival bleeding, bruising, other rated : absent / present : mild , moderate or severe), lung disease, neurological disease

The biological status:

hemoglobin (g/dl); leukocytes (cells/mm³); platelets (mm³); ACE (angiotensin converting enzyme (U/l); ferritin (mg/l); chitotriosidase (nmol / h / ml); CCL18 (ng/ml), vitamin D (nmol/l), vitamin B12 (pmol/l); SGOT/AST (U/l), SGPT/ALT (U/l), GGT (U/l), alkaline phosphatase (U/l), triglycerides (mmol / l), total cholesterol (mmol/l) gamma globulin (g/l) serum calcium (mmol/l) presence or absence of a monoclonal peak and type if any.

The review will be done on the MRI that the treating physician has addressed for a central review radiological center via the CETG after blinding of the documents.

As previously, the quality of the MRI is evaluated and classified in three categories: Optimal, sub optimal and not assessable according the following definition:

- Optimal: Sufficient anatomical coverage, good image quality with no to minimal image artifacts and compliance with the imaging protocol
- Suboptimal: Sufficient anatomical coverage, presence of moderate image artifacts and/or minor deviations to the imaging protocol, with minimal impact on the analysis
- Not assessable: Insufficient anatomical coverage and/or presence of strong image artifacts and/or severe deviations to the imaging protocol, which would lead to an unreliable analysis.

Spleen/Liver:

TEST	DESCRIPTION	FORMAT/VALUES

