8.3 Analysis Populations

All patients included in the study will be included in the statistical analysis

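### Liver and spleen MRI volumes are compared over time without allowing for body size although patients of any age may enter, so growth in a child can hide a real reduction

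*Protocol*

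**What the plan says.** Section 3.2 lists liver volume and spleen volume among the secondary MRI endpoints, in cubic metres. The reading tables in sections 6.6 and 6.7 record the same quantities in cubic millimetres. Nowhere is a volume expressed per kg of body weight or as a multiple of normal.

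Section 8.6 names the comparison for each organ: "changes in liver measurements will be compare using analysis of variance on repeated series" and "changes in spleen measurements will be compare using analysis of variance on repeated series". More generally, it says that changes are "described by mean and standard deviation or percentage changes", and it allows a Wilcoxon test where normality is not shown. No body-size or age term appears.

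Section 5.1 admits patients of any age and plans assent for those under 18. Section 8.3 states: "All patients included in the study will be included in the statistical analysis". No section presents children separately.

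Under section 4.12 the reference MRI is the one closest to the start of VPRIV, from five years before to three months after. Follow-up runs to one year after inclusion, and routine MRI is about every two years.

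Weight and height are clinical criteria in section 3.2. Section 4.1 collects clinical data within three months either side of each MRI, and section 6.7 records them "whenever they are available in patient's dossiers". They are not linked to the volumes.

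**The concern.** A child's liver and spleen are expected to grow as the child grows. A raw volume measured some years after the reference scan therefore mixes growth, which pushes it up, with any treatment-related shrinkage, which pushes it down. A volume that has not changed in a child who has grown means the organ has become smaller relative to the body, but the planned comparison reads it as no change. Growth between a reference scan taken before treatment and the first infusion is also counted as change.

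The direction is known: this is bias towards no effect, not added noise. Section 1.3 gives quantified organ volume as one of the two kinds of data the study will provide, the other being bone alteration, and says the results will partly answer a request from the French health authority. The yes/no endpoints for hepatomegaly and splenomegaly are a cruder safeguard and do not supply that quantified result.

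**Working it through.** The protocol states no effect size, standard deviation or power for these endpoints, so there is no planned figure to reproduce. The check is a break-even calculation followed by a cohort illustration.

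**One child.** Let g be weight at the later MRI divided by weight at the reference MRI, and r the fall in volume per kg. By identity:

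raw volume ratio = (1 − r) × g

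The raw volume shows no fall when (1 − r) × g ≥ 1, that is, when r ≤ 1 − 1/g.

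| Weight ratio g | Largest per-kg fall fully hidden | Raw reading of a 37.5% per-kg fall |
|---|---|---|
| 1.25 | 1 − 1/1.25 = 20% | 0.625 × 1.25 = 0.781, i.e. −22% |
| 1.5 | 1 − 1/1.5 = 33% | 0.625 × 1.5 = 0.9375, i.e. −6% |
| 2 | 1 − 1/2 = 50% | 0.625 × 2 = 1.25, i.e. +25% |

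To put time on this, assume weight gain of 5, 8 or 10% a year. A 20% per-kg fall needs g = 1.25 to be cancelled, which takes 4.6, 2.9 or 2.3 years. A 50% fall needs g = 2, which takes 14.2, 9.0 or 7.3 years, so large falls are mostly diluted, not cancelled.

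**Cohort, change in mean raw volume (the scale of the named ANOVA).** Assumptions, none of them from the protocol:
- Normal volume is proportional to weight.
- Everyone starts at 1.6 times normal.
- Adults weigh 70 kg and fall by 20%.
- Children start at 20 kg and reach 1.0 times normal, a per-kg fall of 37.5%.

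In weight-proportional units an adult goes from 70 × 1.6 = 112 to 89.6. A child goes from 20 × 1.6 = 32 to 20 without growth, 30 at g = 1.5, or 40 at g = 2. With a share p of children:

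change = [(1 − p) × 89.6 + p × child after] / [(1 − p) × 112 + p × 32] − 1

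For p = 0.10 and g = 2: (80.64 + 4.00)/(100.8 + 3.2) − 1 = 84.64/104 − 1 = −18.6%. The gap is the difference from the no-growth column.

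| Share of children | No growth | g = 1.5 (gap, points) | g = 2 (gap, points) |
|---|---|---|---|
| 0% | −20.0% | −20.0% (0) | −20.0% (0) |
| 5% | −20.3% | −19.8% (0.5) | −19.3% (0.9) |
| 10% | −20.5% | −19.6% (1.0) | −18.6% (1.9) |
| 20% | −21.2% | −19.1% (2.1) | −17.0% (4.2) |

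**Cohort, mean of individual percentage changes.** Section 8.6 leaves open whether these are averaged. If they are, each child counts as much as an adult:
- True per-kg mean = (1 − p)(−20) + p(−37.5)
- Raw mean = (1 − p)(−20) + p(−6.25) at g = 1.5, or with p(+25) at g = 2

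| Share of children | Per-kg mean | Raw mean, g = 1.5 | Raw mean, g = 2 |
|---|---|---|---|
| 0% | −20.0% | −20.0% | −20.0% |
| 5% | −20.9% | −19.3% | −17.8% |
| 10% | −21.8% | −18.6% | −15.5% |
| 20% | −23.5% | −17.3% | −11.0% |

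**Sensitivity.** If children fall by the same 20% per kg as adults, a child goes from 32 to 25.6 × g, that is 38.4 or 51.2, and the benchmark is −20% throughout. On mean raw volume the gap at 5, 10 and 20% children is then 0.6, 1.2 and 2.7 points (g = 1.5), or 1.2, 2.5 and 5.3 points (g = 2).

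**The case against.** The strongest reply is that this belongs in the statistical analysis plan. Section 8.1 says a detailed plan will follow, weight is already collected, and nothing in the protocol forbids a derived per-kg volume. That is true, but the protocol does not leave the matter blank: section 3.2 sets the scale and section 8.6 names the comparison. A later plan that followed both to the letter would contain the problem.

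It can also be said that the secondary objective is only descriptive, and that raw volume correctly describes raw volume. That stands as far as it goes. But section 8.6 tests the change over time, and section 1.3 wants the data in order to judge the impact of treatment.

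The Wilcoxon alternative means that the mean-volume figures above apply only to the ANOVA route. A rank test on raw volumes, however, still contains growth.

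The objection on size largely stands. On mean raw volume the cohort gaps are small and the direction of the result never changes. The larger gaps need individual percentage changes to be averaged. Eligibility at any age shows that children may enter, not that they will, and five years before treatment is the outer limit for the reference scan.

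The logistic regression in section 8.6 could include age or weight, but it would not rescale the volumes.

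Finally, a per-kg scale has its own distortion in adults. An unchanged liver reads 1/1.1 − 1 = −9% per kg after a 10% weight gain, and 1/0.9 − 1 = +11% after a 10% loss. That is a reason to report both scales, not to omit one.

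**Conclusion.** The concern holds. For an individual growing child, the planned comparison understates a reduction relative to body size and can cancel or reverse it. The relation between raw and per-kg change is exact; reading the per-kg change as the true one assumes that normal organ size rises in proportion to weight.

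For the cohort, the effect runs from nothing, if no growing children are included, to roughly 0.5 to 5 points on mean volume in the illustrations, and up to 23.5 − 11.0 = 12.5 points if individual percentage changes are averaged. With 40 to 50 patients expected (section 8.2), a 10% share would be 4 to 5 children. The shares, weights, growth and size of fall are all assumptions. With few children the effect is likely to be small.

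Only the secondary volume endpoints are affected. The change should be made because it is cheap and the direction of the bias is known, but it does not threaten the study's main result.

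**What to change.** In sections 3.2 and 8.6, add liver and spleen volume per kg as an analysed endpoint, using the body weight nearest each MRI within the three-month window already planned. Report it beside raw volume, and state in advance that both scales will always be shown.

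Present patients under 18 at the reference MRI separately and descriptively only, since they may be few. On age, section 6.5 says "The age that will be collected is the age of patient at" VPRIV initiation. State, therefore, that age at the reference MRI is derived as age at initiation minus the time from that MRI to initiation (plus the interval if the MRI came after initiation). Age at initiation alone is not enough: a patient aged 18 to 22 at initiation can have been under 18 at a scan up to five years earlier.

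The cost is wording and two derived variables from data already planned. Patients with no recorded weight near an MRI drop out of the per-kg analysis, so report how many.

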8.2 Determination of Sample Size

There is no predefined sample size but in order to reflect daily practices, the study may include all patients presenting type 1 Gaucher disease and treated with VPRIV® in France.

So, based on data from the CETG, a sample size from 40 to 50 patients could be expected.

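### Section 8.6 assigns the monoclonal peak, a present/absent variable, to repeated-series ANOVA, against the protocol's own rule for matching tests to variables

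*Protocol*

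**What the plan says.** Section 3.2 lists the variable among the biological criteria as "presence or absence of a monoclonal peak and the type if any". Section 6.7, on what is recorded around each MRI, repeats this as "presence or absence of a monoclonal peak and type if any", and the synopsis agrees. No unit or concentration is given for the peak.

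Section 8.6 states a general rule: "Comparisons shall be made by analysis of variance on repeated series for quantitative variables", with a signed-rank test if normality is not demonstrated. Other criteria are to be compared "by McNemar tests or rank tests on repeated series for quantitative or ordinal criteria". Present/absent imaging findings follow that second branch, for example: "Changes over time in splenomegaly, presence of nodules or infarct will be analysed using Mac Nemar test".

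The laboratory sentence, later in the same section, names 20 parameters. The first 19 are measured quantities and the last is the peak. All 20 receive one method: "monoclonal peak) will be analysed using variance analysis on repeated series". That sentence offers no alternative.

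**The concern.** A present/absent variable has no normal error model, and the type of a peak is nominal, so analysis of variance does not fit either part of this endpoint. The protocol already recognises the distinction for hepatomegaly, splenomegaly, nodules, lithiasis and infarct, which go to McNemar. The peak appears to have been swept in with the continuous values around it.

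The protocol does not leave this choice open. It fixes a method, so an analysis plan that follows section 8.6 runs ANOVA on 0/1 codes, and one that corrects it departs from the protocol. At stake is a p-value for this one variable that may rest on the wrong test when few patients gain or lose a peak.

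**Working it through.** **Match of variable and method.**

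| Item | Section | Content |
|---|---|---|
| Nature of the variable | 3.2, 6.7 | Present/absent, plus type |
| Rule for ANOVA | 8.6 | Quantitative variables |
| Method for similar present/absent findings | 8.6 | McNemar |
| Method for the peak | 8.6 | Repeated-series ANOVA only |

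The last row disagrees with the first three.

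**Can the choice matter?** The protocol gives no significance level, effect size or result for this variable, so there is no stated figure to reproduce. The following is an illustration.

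Inputs: n = 40 to 50, from section 8.2 ("a sample size from 40 to 50 patients could be expected"). Assumptions that are not in the protocol: two time points, complete pairs and a two-sided 5% level. Let b be the number of patients who lose the peak and c the number who gain it.

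- ANOVA with two times is the square of the paired t test: mean m = (b − c)/n, sum of squares SS = (b + c) − n·m², t = m / √[SS/((n − 1)n)] on n − 1 degrees of freedom.
- Exact McNemar: p = 2·P[Bin(b + c, ½) ≤ min(b, c)].
- Ordinary uncorrected McNemar: χ² = (b − c)²/(b + c) on 1 degree of freedom.

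Example with n = 40, b = 4, c = 0: m = 0.1; SS = 4 − 40 × 0.01 = 3.6; t = 0.1/√[3.6/(39 × 40)] = 2.08; p = 0.044. Exact McNemar gives 2 × (½)⁴ = 0.125. Ordinary McNemar gives χ² = 16/4 = 4, p = 0.046.

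| Losses v gains | ANOVA p (n = 40 to 50) | Exact McNemar p | Ordinary McNemar p |
|---|---|---|---|
| 4 v 0 | 0.044 | 0.125 | 0.046 |
| 5 v 0 | 0.023 to 0.024 | 0.0625 | 0.025 |
| 7 v 1 | 0.032 | 0.070 | 0.034 |
| 6 v 0 | 0.012 to 0.013 | 0.031 | 0.014 |

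In the first three rows ANOVA and exact McNemar fall on opposite sides of 5%. ANOVA and ordinary McNemar agree in every row.

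**Actual type I error.** This was found by enumerating all outcomes for n = 40, 45 and 50, with equal gain and loss probabilities of 2.5%, 5%, 10% and 15% each (assumed). ANOVA rejects with probability 0.014 to 0.047, and exact McNemar with probability 0.0004 to 0.028. Neither exceeds 5%.

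**The case against.** The strongest reply is that little would change in practice.

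- **Size of the effect.** The gap in the table is between exact and asymptotic testing. Section 8.6 names McNemar without saying exact, and ordinary McNemar gives p-values within about 0.002 of ANOVA. This stands: moving the peak to McNemar affects the conclusion only if the exact form is used when changes are few.
- **General wording.** Section 8.6 also lets the choice follow the variable: "ANOVA on repeated series or Wilcoxon rank test, depending on the nature and distributions of the studied variables". On paired 0/1 data all non-zero differences have the same size, so an exact signed-rank test with zeros dropped is the sign test, which is exact McNemar. The general rule could therefore lead to a suitable analysis. But the laboratory sentence is more specific and names ANOVA alone, so the conflict remains.
- **Deferral.** Section 8.1 promises a detailed analysis plan, which may already correct this. That does not make the protocol's own statement consistent.

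A reader might infer more than the document supports:

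- That ANOVA inflates false positives here. The enumeration does not show this.
- That only an exact test is valid. The exact test is the safer choice with few discordant pairs, but it is conservative.
- That the peak would be described by a mean of 0/1 codes. Section 8.6 describes categorical variables by frequency and percentage.
- That peaks are rare in this cohort. The protocol gives no prevalence.

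**Conclusion.** The point holds as an internal inconsistency. By the protocol's own definition the peak is present/absent with a type, and by its own rule ANOVA is for quantitative variables, yet ANOVA is the only method named for the peak.

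The weight is minor: one of 20 laboratory entries, secondary/exploratory, in a study whose stated aims are descriptive. The primary endpoint is not affected. The practical consequence is conditional: if only a handful of patients change status, the conclusion can depend on the test, as with 4 losses and 0 gains. That illustration rests on the assumed 5% level, two time points and complete pairs in 40 to 50 patients. It shows sensitivity to the test, not an error rate above the nominal level.

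**What to change.** In section 8.6:

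1. Remove the monoclonal peak from the ANOVA list.
2. Compare status at the reference and final times by McNemar, exact when discordant pairs are few, and show the paired 2x2 table.
3. If more than two times are compared, use Cochran's Q or a repeated-measures logistic model. The sentence concerns change over time, and section 4.1 collects biology around each MRI, so a reference-to-final comparison alone would drop the intermediate times. Cochran's Q needs every patient at every time compared; the logistic model does not.
4. Report the type of peak by frequency.
5. In the same edit, correct the clause that assigns McNemar or rank tests to quantitative or ordinal criteria. The first adjective is probably a slip for qualitative, and as written the clause does not name binary variables.

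The cost is a line or two of text. No new data are needed.

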4 STUDY PLAN

4.1 Data collection and transmission

All data entered will be used for analysis purposes and results will be submitted to inform regulatory agencies. Patient care and management is freely determined by the participating physician, in the framework of an observational study reflecting the daily medical practice. The clinical data, the results of routine clinical and laboratory testing that are part of standard medical care for patients with Gaucher disease will be collected from the medical record of the patient :

- Socio-demographic characteristics
- History of the disease and context of diagnosis
- Medical background
- MRI: abdominal and bone, as defined below
- Clinical data available in the range from 3 months before or after each MRI
- Biological data available in the range from 3 months before or after each MRI
- Treatment with VPRIV® (velaglucerase alfa), including the doses and regimens

4.2 The MRI images collected during the study:

The MRIs performed in the patient's usual medical follow-up for its Gaucher disease (abdominal MRI (liver and spleen) and bone MRI (back injury pelvis, lower limbs) and / or whole-body MRI) will be collected. Among the MRIs available in the patient's medical records, MRIs will be collected the following:

- Reference MRI: MRI closest to the date of initiation of VPRIV® in the five years preceding the start of treatment or within three months after initiation of VPRIV®.
- MRIs of the retrospective phase of the study: All MRIs available between the reference MRI and the inclusion date of the patient.
- MRIs of the prospective phase of the study: all the MRIs that will be realized during the prospective phase of the study, that is to say, during the year following the date patient inclusion in the study.

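### Section 8.6 names repeated-series ANOVA for laboratory values and organ measurements, a method that in its classical form drops incomplete patients, although incomplete series are to be expected here; a mixed model would be a cheap improvement

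*Protocol*

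**What the plan says.** Section 8.6 of the protocol sets out the secondary analyses in layers.

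- **General rule.** All secondary criteria, including the biological ones, are compared between times by "ANOVA on repeated series or Wilcoxon rank test, depending on the nature and distributions of the studied variables". A later sentence has quantitative variables compared by repeated-series ANOVA, or "by Wilcoxon signed rank tests if normality is not demonstrated".
- **Specific sentences.** For the organs, "changes in liver measurements will be compare using analysis of variance on repeated series", and the spleen sentence names the same method. For a list of 20 biological parameters, changes over time "will be analysed using variance analysis on repeated series". These sentences give no alternative.
- **Description.** "The evolutions of these criteria at the different periods when they are collected are described by mean and standard deviation or percentage changes". The same paragraph also plans 95% confidence intervals.

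On data collection, section 4.1 limits laboratory data to "Biological data available in the range from 3 months before or after each MRI". Section 6.7 says that "the following information will be recorded whenever they are available in patient's dossiers". Section 4.2 collects every routine MRI from the reference scan to inclusion and any scan in the following year. Section 4.12 notes that routine MRI takes place about every 2 years. On size, section 8.2 says "a sample size from 40 to 50 patients could be expected". Section 8.3 puts all included patients in the analysis.

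**The concern.** Classical repeated-measures ANOVA needs a balanced table, with every patient measured at every occasion. A patient with one gap is removed entirely, including the values that were recorded.

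The study orders no tests, so gaps in laboratory values follow from its design. The occasions are also unbalanced. Patients start treatment at different dates and have different numbers of scans, and a one-year prospective phase need not contain a scan that routine care performs every 2 years. This second source affects organ volumes as well, even though they are read centrally from each scan.

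The tests of change could therefore rest on subsets that are smaller than the cohort, differ from marker to marker, and favour the patients tested most often. Section 8.3 intends all included patients to be analysed, and the named method does not deliver that when series are incomplete.

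**Working it through.** The protocol states no completeness rate, no number of occasions and no power calculation for these endpoints, so there is no planned figure to reproduce. What follows is a sensitivity calculation.

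**Inputs.** N = 40 to 50 (protocol 8.2). Assumed: p, the chance that a value is available at one occasion; k, the number of occasions; independence between occasions.

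**Step 1: complete series.** Expected number = N × p^k.

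| k | p = 0.7 | p = 0.8 | p = 0.9 |
|---|---|---|---|
| 2 | 19.6-24.5 | 25.6-32.0 | 32.4-40.5 |
| 3 | 13.7-17.1 | 20.5-25.6 | 29.2-36.5 |
| 4 | 9.6-12.0 | 16.4-20.5 | 26.2-32.8 |

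For k = 3 and p = 0.7, for example, p^k = 0.343, so 40 × 0.343 = 13.7 and 50 × 0.343 = 17.1.

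**Step 2: when would most patients be lost?** More than half are expected to drop out when p^k < 0.5, that is when p < 0.5^(1/k). The limits are 0.71 (k = 2), 0.79 (k = 3) and 0.84 (k = 4).

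**Step 3: clustered gaps.** Suppose half of the patients always have a value and the other half have one with probability 0.4. Average availability is 0.5 + 0.5 × 0.4 = 0.70. With k = 3 the share with complete series is 0.5 + 0.5 × 0.4³ = 0.532, against 0.343 under independence.

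**Step 4: precision.** Take 45 patients, equal correlation of 0.5 to 0.7 between occasions, and values missing at random. The standard error of the last-minus-first change is compared with that of generalised least squares (the mixed model) on all available values, averaged over simulated missingness patterns.

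| k, p | Complete series / mixed model | Simple first-last pairs / mixed model |
|---|---|---|
| 2, 0.7 | 1.06-1.10 | 1.06-1.10 |
| 3, 0.7 | 1.33-1.36 | 1.10-1.13 |
| 3, 0.9 | 1.09 | 1.03-1.04 |
| 4, 0.7 | about 1.65 | 1.13-1.15 |

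Most of the penalty at k = 3 or 4 comes from discarding patients who have both end values but lack a middle one. With k = 2 the two approaches coincide.

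**Step 5: do the other parts of 8.6 cover the gap?** The Wilcoxon route applies when a variable's type or distribution calls for it. A roughly normal marker with many gaps stays with ANOVA. The per-period means use every value, but when different patients contribute at each period, a difference between two such means is not an estimate of within-patient change.

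**The case against.** The main objections, and what stands of each:

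- **8.6 does not rely on ANOVA alone.** True of the section as a whole. The general rule offers Wilcoxon tests for the same criteria, and a signed-rank test needs only two values per patient. A reader might infer from the biological-parameters sentence that no other analysis exists; the section does not support that. The switch, however, is not tied to missing data.
- **The secondary objectives are descriptive, and per-period description needs no complete series.** This stands. A reader might infer that the cohort would go undescribed. That is not so. What suffers is the estimate and test of within-patient change.
- **No loss figure is given.** This stands. A reader might infer that most of the 40-50 patients would drop out. The protocol gives neither availability nor number of occasions, and at p = 0.9 most patients stay for k = 2 to 4.
- **Organ volumes do not depend on laboratory files.** This stands. For them only the varying number and timing of scans matters, so the availability rates above should not be carried over.
- **CCL18 is a likely sparse marker.** It is collected, but it is not in the list assigned to ANOVA and falls under the general rule.
- **Missing-data handling belongs in the analysis plan.** Partly. The protocol states no complete-case rule, and the later plan could read the term as a mixed model. The point here is that the protocol names a method that suits these data poorly, not that detail is missing.

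**Conclusion.** The point holds as a modest one. Section 8.6 names, for 20 biological parameters and for liver and spleen measurements, a method that in its classical form cannot use incomplete series, in a study where incomplete series are to be expected. No method named in 8.6 uses all available values to estimate within-patient change.

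The size is conditional. With 3 occasions and independent availability, complete series number about 14-17 of 40-50 at p = 0.7 and 29-36 at p = 0.9, and more if gaps cluster. The standard error for first-to-last change is then about 1.33-1.36 or 1.09 times that of a mixed model. Measured against what a simple paired comparison already achieves, the mixed model's gain at p = 0.7 is smaller, a ratio of about 1.1. These figures rest on assumed availability, number of occasions and correlation, and none of them comes from the protocol. Only secondary endpoints are affected.

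**What to change.** In section 8.6, for quantitative laboratory values and for liver and spleen measurements, replace repeated-series ANOVA with a linear mixed model for repeated measures:

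- a patient random effect or a repeated covariance structure;
- time since VPRIV initiation as a fixed effect, either in defined windows or as continuous time, because patients share no common scan dates;
- every available value included;
- the estimated change reported with its 95% CI, and the number of patients and of values at each time.

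The monoclonal peak is recorded as present or absent, so it needs to be taken out of the quantitative list.

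The cost is one sentence in 8.6 and its counterpart in the analysis plan, with no new data. The small downside is reliance on a missing-at-random assumption, which is generally weaker than what a complete-case analysis needs.
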